## APPENDIX 1. PROGRAMMING CONVENTIONS FOR OUTPUTS

CCI  
[Redacted]

Outputs will be presented according to the following output conventions.

### 1. ABBREVIATIONS

- ASCII American standard code for information interchange file format
- CGM Computer graphics metafile
- ODS Output Delivery System
- RTF Rich text file format
- PDF Portable Document Format

### 2. INTRODUCTION

This document applies to standards used for outputting tables, listings and figures. It is intended to provide specifications to guide the statistician or statistical programmer in setting up specifications for programming tables, listings and figures.

### 3. OUTPUT FILE NAMING CONVENTIONS

File names should only consist of uppercase letters, lowercase letters, digits (0 to 9) and underscores. A period should only be used to indicate a separator between the file name and the extension. No spaces, other special characters or punctuation marks are permitted.

As far as possible, output files should be in RTF format, although .DOC files are also permitted.

The program, program log and output file name should reflect the type and number of the statistical output. If this is not possible, then the output name should be at least as descriptive as possible. A prefix can be used to distinguish between a Table, Listing and Figure document ('T' for table, 'L' for listing and 'F' for figure). If there is only 1 digit in the number of the table, listing or figure in the place where 2 digits are possible, a leading zero should be added in the file name to make sorting consistent with the sequence (eg T14\_3\_01\_1\_disp.RTF)

### 4. PAPER SIZE, ORIENTATION AND MARGINS

The size of paper will be Letter for the United States.

The page orientation should be landscape.

Margins should provide at least 1 inch (2.54 centimeters) of white space all around the page, regardless of the paper size.

---

Document:	CCI	Version Number:	Final 2.0
Author:	PPD	Version Date:	12Apr2019

Template No: CCI Reference: CCI  
Effective Date: 01Apr2016

Copyright © 2009, 2010, 2012, 2016 CCI All rights reserved.  
The contents of this document are confidential and proprietary to CCI. Unauthorized use, disclosure or reproduction is strictly prohibited.

**Analysis Plan**

The number of columns per page (linesize) should be 145 for A4 and 134 for Letter.

The number of rows per page (pagesize) should be 49 for A4 and 51 for Letter.

## 5. FONTS

The font type 'Courier New' should be used as a default for tables and listings, with a font size of 8. The font color should be black. No bolding, underlining, italics or subscripting should be permitted. Super-scripts will be avoided. Single spacing should be used for all text.

## 6. HEADER INFORMATION

Headers should be defined as follows:

- The header should be placed at the top of the page (same place on each page) regardless of the size or orientation of the table or listing
- The protocol number and treatment should appear in row 1, left-aligned, and the page number (in the format of Page X of Y) should appear as right-aligned
- The indication should appear in row 2, left-aligned, and the customer name should be right-aligned
- Row 3 should be blank
- The output identification number should appear in row 4, centered
- The output title should start in row 5, centered
- The output population should appear in row 6, centered. The population should be spelled out in full, e.g. Intention-to-Treat in preference to ITT.
- Row 7 should be a continuous row of underscores ('\_') (the number of underscores should equal the linesize)
- Row 8 should be a blank line
- Mixed case should be used for titles
- The output titles should be designed so that they are arranged consistently through all outputs. For example, content (eg Vital Signs) followed by metric (eg CFB) e.g. Vital Signs – CFB.
- Titles should not contain quotation marks or footnote references
- The column headings should be underlined with a row of underscores ('\_')
- Column headings spanning more than one column should be underlined and have underscores on either side of the title and should be centered
- Column headings containing numbers should be centered
- Column headings should be in sentence case
- In general, the population count should appear in the column header in the form "(N=XXX)"
- "Statistic" should be the column header over n, Mean, SE, n (%) etc.
- As a rule, all columns should have column headings.

Document: CCI

Author: PPD

Version Number:

Version Date:

Final 2.0  
12Apr2019

Template No: CCI

Effective Date: 01Apr2016

Reference: CCI

Copyright © 2009, 2010, 2012, 2016 CCI All rights reserved.

The contents of this document are confidential and proprietary to CCI. Unauthorized use, disclosure or reproduction is strictly prohibited.

## 7. TABLE AND LISTING OUTPUT CONVENTIONS

## General:

- The first row in the body of the table or listing should be blank
- The left hand column should start in column 1. No indenting or centering of the output should occur.
- Rounding should be done with the SAS function ROUND.
- Numbers in tables should be rounded, not truncated.
- Alphanumeric output should be left aligned.
- Numbers should be decimal point aligned.
- Whole numbers should be right aligned.
- Text values should be left aligned.
- The first letter of a text entry should be capitalized
- Listings of adverse events, concomitant medications, medical histories etc. should be sorted in chronological order within subject, with earliest adverse event, medication or history coming first.
- The study drug should appear first in tables with treatments as columns
- In general, only present totals (across treatment groups) at baseline/randomization, and do not present them post randomization.
- If possible, include 100% frequencies in the table shell, so that it is clear what the denominator is for percentage calculations.
- All listing outputs should be sorted (preferably by Treatment, Site Number and Subject Number).
- Do not use superscripts and subscripts
- All variables that are output in the eCRF (which have data present) should appear in the listings
- The width of the entire output should match the linesize

## Univariate Statistics:

- Statistics should be presented in the same order across tables (i.e., n, Mean, SD, Median, Minimum, Maximum)
- Table statistics should line up under the N part of the (N=XXX) in the table header. All decimal points should line up.
- If the original data has N decimal places, then the summary statistics should have the following decimal places:

Minimum and maximum: N

Mean and median: N + 1

SD and CV: N + 2

Document:

CCI

Author:

PPD

Version Number:

Version Date:

Final 2.0  
12Apr2019

Template No: CCI

Effective Date: 01Apr2016

Reference: CCI

Copyright © 2009, 2010, 2012, 2016 CCI. All rights reserved.

The contents of this document are confidential and proprietary to CCI. Unauthorized use, disclosure or reproduction is strictly prohibited.

---

**Analysis Plan**

---

CV%: N, but with a maximum number of 1 decimal place

The maximum number of decimal places should be 4 for statistics other than CV%.

Frequencies and percentages (n and %):

- Percent values should be reported inside parentheses, with one space between the count and the left parenthesis of the percentage. Parentheses should be justified to accept a maximum of 100.0 as a value and padded with blank space if the percent is less than 100.0. An example is given below:

77 (100.0%)

50 ( 64.9%)

0 ( 0.0%)

Confidence Intervals:

- As a rule confidence intervals are output to one place more than the raw data. Standard errors are output to two places more than the raw data.
- Boundary values of confidence intervals should be separated by a comma.
- Boundary values should be padded as necessary to accept negative values and to allow alignment of the decimal place.
- Boundary value of -0.00 should be presented as 0.00.
- An example is given below:

(-0.12, -0.10)

( 9.54, 12.91)

P-values:

- P-values should be reported to three decimal places, except values <1.000 but >0.999 will be presented as '>0.999' (e.g., 0.9998 is presented as >0.999); and values <0.001 will be presented as '<0.001' (e.g., 0.0009 is presented as <0.001). Rounding will be applied after the <0.001 and >0.999 rule

Ratios:

- Ratios should be reported to one more decimal place than the original data.

Spacing:

- There must be a minimum of 1 blank space between columns (preferably 2)

---

Document: CCI

Author: PPD

Version Number:

Version Date:

Final 2.0  
12Apr2019

Template No: CCI

Effective Date: 01Apr2016

Reference: CCI

Copyright © 2009, 2010, 2012, 2016 CCI. All rights reserved.

The contents of this document are confidential and proprietary to CCI. Unauthorized use, disclosure or reproduction is strictly prohibited.

---

**Analysis Plan**

---

**Denominators:**

- If a different count other than the population count is used for a denominator (within the table) to calculate percentages, there should be a row in the table that identifies that number “n”.
- Alternatively, a footnote should be included in each table with percentages to indicate the denominator for percentages.

**Missing values**

- A “0” should be used to indicate a zero frequency.
- A blank will be used to indicate missing data in an end-of-text table or subject listing.

**8. FOOTNOTE INFORMATION****Footers should be defined as follows:**

- A continuous line of underscores (‘\_’) will follow the body of the table or listing prior to any footnotes at the bottom of the page
- Table footnotes should be defined using compute statements in the proc report, and should appear directly after the body of the table
- The program path and name should appear as footnote 1 at the bottom of the page, followed on the same line by the date/time stamp
- Footnotes should be left-aligned.
- Footnotes should be in sentence case.
- Only “typewriter” symbols are permitted – eg “\*”, “\$”, “#”, “@”, “&” and “+”.
- The choice of footnote symbols should be consistent. E.g. if you have the footnote “# indicates last observation carried forward” for one table, the same symbol and footnote should indicate LOCF for all tables.
- If text wraps across more than one line (for a note), the first letter for all lines of text after the first one will be indented to align beneath the first letter of the text in the first line.

**Ordering of footnotes should be as follows:**

- 1.) Abbreviations and definitions
- 2.) Formulae
- 3.) Symbols
- 4.) Specific notes

- Common notes from table to table should appear in the same order.
- The symbols should appear in the same order as what they are defined in the table or listing, from left to right.

Document: CCI

Author: PPD

Version Number:

Version Date:

Final 2.0  
12Apr2019

Template No: CCI

Effective Date: 01Apr2016

Reference: CCI

Copyright © 2009, 2010, 2012, 2016 CCI. All rights reserved.

The contents of this document are confidential and proprietary to CCI. Unauthorized use, disclosure or reproduction is strictly prohibited.

## Analysis Plan

## 10. PROGRAMMING INSTRUCTIONS

Programming instructions, if required, must appear in blue font at the end of each table or listing shell. Programming instructions, where necessary, should follow the table or listing shells in blue font, beginning with the words "Programming Note" followed by a colon. These include notes on the output, reminders of how to handle missing values, repeat shells for similar tables etc.

**DATES & TIMES**

Depending on data available, dates and times will take the form DDMMYYYY/HH:MM.

**SPELLING FORMAT**

English US

**PRESENTATION OF TREATMENT GROUPS**

For outputs, treatment groups will be represented as follows and in that order:

Treatment Group	For Tables, Listings and Graphs
Immune Globulin (Human), 10% Caprylate/Chromatography Purified (IGIV-C) loading dose of 2 g/kg followed by 12 maintenance dosages of 1 g/kg every 3 weeks	IGIV-C
Matched Placebo	Placebo
Total	Total

**PRESENTATION OF VISITS**

For outputs, visits will be represented as follows and in that order. Where necessary to uniquely identify data records, additional time points will be included in the outputs.

Long Name (default)	Short Name
Screening	Scr
Baseline	BL

Document: CCI

Author: PPD

Version Number:

Version Date:

Final 2.0  
12Apr2019

Template No: CCI

Effective Date: 01Apr2016

Reference: CCI

Copyright © 2009, 2010, 2012, 2016 CCI. All rights reserved.

The contents of this document are confidential and proprietary to CCI. Unauthorized use, disclosure or reproduction is strictly prohibited.

## Analysis Plan

Long Name (default)	Short Name
Week 3	WK3
Week 6	WK6
Week 9	WK9
Week 12	WK12
Week 15	WK15
Week 18	WK18
Week 21	WK21
Week 24	WK24
Week 27	WK27
Week 30	WK30
Week 33	WK33
Week 36	WK36
Week 39	WK39
Week 42	WK42
Week 45	WK45
Early Termination 1	ET1
Early Termination 2	ET2

## LISTINGS

All listings will be ordered by the following (unless otherwise indicated in the template):

- randomized treatment group (or treatment received if it's a safety output), first by active and then placebo
- subject ID (which in this study includes the site ID as the first 3 digits),
- date (where applicable),
- For listings where non-randomized subjects are included, these will appear in a category after the randomized treatment groups labelled 'Not Randomized'.

Document: CCI

Author: PPD

Version Number:

Final 2.0

Version Date:

12Apr2019

Template No: CCI

Reference: CCI

Effective Date: 01Apr2016

Copyright © 2009, 2010, 2012, 2016 CCI. All rights reserved.

The contents of this document are confidential and proprietary to CCI. Unauthorized use, disclosure or reproduction is strictly prohibited.

**APPENDIX 2. PARTIAL DATE CONVENTIONS**

Any imputed AE start date/time will only be used to determine whether an AE is treatment emergent or not. The start and stop dates/times reported on the eCRF will be presented in the listings.

**ALGORITHM FOR TREATMENT EMERGENCE OF ADVERSE EVENTS:**

AE START DATE TIME	STUDY MEDICATION START DATE TIME	ACTION
Known	Known	If start date/time < study med start date/time, then not TEAE If start date/time >= study med start date/time, then TEAE
Partial or Missing	Known	If start date < study med start date, then not TEAE If start date > study med start date, then TEAE If start date = study med start date, then impute AE start time to the latest possible time (i.e. 23:59 if hours and minutes are missing, or 59 minutes past the hour if only minutes are missing). If this imputed date/time is after AE stop date/time, then use AE stop date/time as the imputed AE start date/time. Then: If imputed start date/time < study med start date/time, then not TEAE If imputed start date/time >= study med start date/time, then TEAE
Known	Partial or Missing	If start date < study med start date, then not TEAE If start date > study med start date, then TEAE If start date = study med start date, then impute study med start time as the earliest possible time (i.e. 00:00 if hours and minutes are missing, or 00 minutes past the hour if only minutes are missing). Then: If start date/time < imputed study med start date/time, then not TEAE If start date/time >= imputed study med start date/time, then TEAE

Document: CCI

Author: PPD

Version Number:

Version Date:

Final 2.0  
12Apr2019

Template No: CCI

Effective Date: 01Apr2016

Reference: CCI

Copyright © 2009, 2010, 2012, 2016 CCI. All rights reserved.

The contents of this document are confidential and proprietary to CCI. Unauthorized use, disclosure or reproduction is strictly prohibited.

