4.4.3 Causality of Adverse Event

The investigator is required to provide a causality assessment for each AE reported to the Sponsor. The Sponsor will consider the investigator's causality assessment. Assessment of the causal relationship to the study drug will be made according to the following classifications based on Karch FE, et al (52):

Definite: An event that follows a reasonable temporal sequence from administration of the treatment or in which the treatment level has been established in body fluids or tissues; that follows a known response pattern to the suspected treatment; and that is confirmed by improvement on stopping the treatment (dechallenge), and reappearance of the event on repeated exposure (rechallenge).

Probable: An event that follows a reasonable temporal sequence from administration of the treatment; that follows a known response pattern to the suspected treatment; that is confirmed by dechallenge; and that could not be reasonably explained by the known characteristics of the patient's clinical state.

Possible: An event that follows a reasonable temporal sequence from administration of the treatment that follows a known response pattern to the suspected treatment but that could have been produced by the patient's clinical state or other modes of therapy administered to the patient.

Doubtful/Unlikely: An event that follows a reasonable temporal sequence from administration of the treatment; that does not follow a known response pattern to the suspected treatment; but that could not be reasonably explained by the known characteristics of the patient's clinical state.

Unrelated: Any event that does not meet the criteria above.

The operational tool to decide the AE causal relationship is based on algorithms by Karch and Lasagna and Naranjo et al (53,54).

When an AE is classified, assessing causal relationship by the investigator, as definitive, probable, possible or doubtful/unlikely, the event will be defined as a suspected ADR. A suspected ADR with a causal relationship of "definite" will be defined as an AR. When the causal relationship is labeled "Unrelated," then it will be considered that the AE is not imputable to the study treatment and it is not a suspected ADR.

In addition, when a causal relationship between the study treatment and the AE cannot be ruled out by the investigator and/or Sponsor, it means that the AE cannot be labeled "unrelated."

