For any subject, all AEs that occur at any time, between the beginning of the first infusion of IGIV-C and the final visit of the clinical trial, will be considered TEAEs.

AEs occurring during the actual IP infusions (i.e., from the initiation of the IP infusion on the first day to the completion of the total dosage of IP on the last day) and within 72 hours following the completion of the infusion of the total dosage of IP on the last day, regardless of other factors that may impact a possible causal association with product administration, will be defined as infusional AEs (i.e., an AE temporally associated with an infusion of the IP) and labeled infusional TEAEs (a subset of TEAEs).

For AEs that occur during infusions, the infusion rate in effect at the time of onset of the AE, the time of onset of the AE and the time of AE change materially in intensity and/or resolves will be captured.

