4.4.7.3 MG Events That Are Not Considered AEs

Given that variations in symptoms are an inherent part of the natural history of MG, all recorded information regarding severity of MG manifestations will be considered efficacy data.

For the purpose of this study, variation in MG symptoms will not be considered an AE unless an exacerbation of MG, or MC requires hospitalization. If a subject is hospitalized for MG, it will be reported as an SAE.

4.4.8 Procedures for Eliciting Reports of and for Recording and Reporting Adverse Events and Suspected Adverse Drug Reactions

The occurrence and follow-up details of all AEs experienced by any of the subjects during the clinical trial, from signature of the *Clinical Trial Written Informed Consent Form* to the last follow-up visit, will be recorded on the AE eCRF entry and in the subject's medical record. If no AE has occurred during the study period, this should also be indicated in the eCRF.

At each visit, AEs will be elicited by asking the individual a non-leading question such as "Do you feel different in any way since the last visit?" Moreover, AEs will also be collected through directly observed events or spontaneously volunteered by the subject. Clearly related signs, symptoms and abnormal diagnostic procedures should preferably be grouped together and recorded as a single diagnosis or syndrome wherever possible. It is responsibility of the investigator to ensure that AEs are appropriately recorded.

The following variables must be recorded on the AE eCRF entry:

- 1. the verbatim term (a diagnosis is preferred)
- 2. date/time of onset
- 3. date/time of resolution
- 4. severity (mild, moderate, severe)
- 5. causality (unrelated, doubtful/unlikely, possible, probable, definite)*
- 6. seriousness (yes, no)
- 7. action taken (with regard to IP)
- 8. other action (to treat the event)
- 9. outcome and sequel (follow-up on AE) *AEs occurring before subject's exposure to IP will be always labeled as "unrelated."

For AEs that occur during infusions, the infusion rate in effect at the time of onset of the AE, the time of onset of the AE and the time of AE change materially in intensity and/or resolves will be captured the eCRF entry.

In addition to the investigator's own description of the AEs, each AE will be encoded by the Sponsor or CRO according to the Medical Dictionary for Regulatory Activities (MedDRA®).

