5.1.4 Safety Analyses

The safety analysis will be based on safety population.

The safety analyses will be addressed by listing and tabulation of AEs (includes suspected ADRs), vital signs, physical assessments and clinical laboratory tests. Data will be described using descriptive analyses.

Adverse events:

Safety analysis will be primarily focused on a descriptive analysis of suspected ADRs. Safety assessment will be based on the prevalence of suspected ADRs that occurred during the clinical trial.

AEs will be coded and classified using MedDRA terms (system organ class and preferred terms).

AEs will be classified as TEAEs or non-TEAEs depending on the comparison of AE onset date/time with the start date/time of study treatment with the IP. A TEAE will be defined as an AE which occurs between the beginning of the first infusion of IGIV-C and the final visit of the clinical trial. A non-TEAE will be defined as an AE which occurs prior to the first dose of IP. Non-TEAEs and TEAEs will be summarized separately.

All AEs will be summarized by presenting subject incidences and percentages, and they will also be listed by body systems with subject identification codes.

In addition, TEAEs, including suspected ADRs, will be summarized, system organ class, preferred term, causal-relationship, intensity (severity) and seriousness (serious vs.

non-serious) using descriptive statistics. At each level of summarization, a subject will only be counted once per system organ class or preferred term using the most severe or causal relationship AE.

AEs temporally associated with the infusion of the IP (i.e., infusional AEs, including infusional suspected ADRs), will be summarized by presenting infusion/subject incidences and percentage and listed. In addition, the infusion rate in effect at the time of onset of the AE, the time the AE is first reported and the time the AE changes materially in intensity and/or resolves will be also reported and listed.

Subjects with deaths, SAEs, suspected ADRs and AEs leading to premature discontinuation from the study will be listed and presented in a narrative form.

AEs for which the investigator causality assessment is missing or undetermined will be individually listed.

Vital signs:

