**17.1. ADVERSE EVENTS**

Adverse Events (AEs) will be coded using MedDRA central coding dictionary, Version 17.1.

Treatment emergent adverse events (TEAEs) are defined as AEs that started on or after the beginning of the first infusion of study medication and prior to the final study visit.

See Appendix 2 for handling of partial or missing dates/times for AEs. In the case where it is not possible to define an AE as treatment emergent or not, the AE will be classified by the worst case; i.e. treatment emergent.

Listings will include TEAEs and Non-TEAEs. Subjects with deaths, serious adverse events (SAEs), suspected adverse drug reactions (ADRs) and AEs leading to premature discontinuation from the study will be listed.

An overall summary of number of subjects and number of events within categories of interest will be provided as specified in the templates.

Document: CCI

Author: PPD

Version Number:

Version Date:

Final 2.0  
12Apr2019

Template No: CCI

Effective Date: 01Apr2016

Reference: CCI

Copyright © 2009, 2010, 2012, 2016 CCI. All rights reserved.

The contents of this document are confidential and proprietary to CCI. Unauthorized use, disclosure or reproduction is strictly prohibited.

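### An AE that begins before the first infusion and worsens after it is left out of the TEAE, suspected ADR, infusional and serious-TEAE summaries unless the site opens a new entry

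*SAP*

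**What the plan says.** Treatment emergence depends on when the AE began. SAP 17.1 states: "Treatment emergent adverse events (TEAEs) are defined as AEs that started on or after the beginning of the first infusion of study medication". With both times known, SAP Appendix 2 applies one test: "If start date/time < study med start date/time, then not TEAE". The SAP inherits this from Protocol 5.1.4, which sorts AEs "depending on the comparison of AE onset date/time with the start date/time of study treatment with the IP" and adds: "A non-TEAE will be defined as an AE which occurs prior to the first dose of IP".

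Causality is fixed separately. The note under the list of AE variables in Protocol 4.4.8 reads "AEs occurring before subject's exposure to IP will be always labeled as" unrelated. Protocol 4.4.3 gives the consequence of that rating: "then it will be considered that the AE is not imputable to the study treatment and it is not a suspected ADR".

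On change over time, Protocol 4.4.3 and 4.4.8 provide that "the time of AE change materially in intensity and/or resolves will be captured", but only for AEs that occur during infusions. Neither document says what happens to the classification when an AE already present at dosing gets worse, and neither asks sites to enter such a worsening as a new AE.

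**The concern.** AEs are collected from consent (Protocol 4.3.1), and Screening lasts three weeks, so the database will hold AEs that started before the 2 g/kg loading dose. If one of these is ongoing at dosing and then becomes severe or serious, the worsening is a post-treatment event that the safety objective should pick up. Onset-only classification files it by its earlier, milder start.

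The summaries it drops out of are the ones a reader consults first. Protocol 5.1.4 says the safety analysis centres on suspected ADRs, and the infusional and serious-event tables in the SAP are both built on TEAEs. With about 30 subjects per arm, one misfiled serious event would be noticeable.

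**Working it through.** The plan states no figure on this point, so the check is a trace of the rules.

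Test case (constructed): a mild, non-serious AE starts on Day -5, is ongoing at the first infusion, and becomes severe and serious 12 hours after the loading dose is complete. The site keeps one AE entry.

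1. **TEAE?** The start precedes the first infusion, so under SAP Appendix 2 it is not a TEAE. The later worsening is not an input to the rule.
2. **Suspected ADR or AR?** Under the note in Protocol 4.4.8 it is rated unrelated. Under Protocol 4.4.3 an unrelated AE is not a suspected ADR, and ARs are a subset of suspected ADRs. So neither.
3. **Infusional AE?** SAP 17.1.5 and Protocol 4.4.3 define these as a subset of TEAEs, with a window up to 72 hours after the dosage is complete. The worsening at 12 hours is inside the window, but the event is not a TEAE, so no.
4. **Serious-event table?** SAP 17.1.3 tabulates serious TEAEs by SOC and PT. So no.
5. **Where it does appear.** The separate non-TEAE summary (SAP 17.1.1), the all-AE incidence summary (Protocol 5.1.4), the AE and SAE listings (SAP 17.1 and 17.1.3) and SAE reporting from consent onward (Protocol 4.4.9). If it is flagged on the eCRF as thromboembolic or hemolytic, it also enters the SAP 17.1.6 summaries, which carry no stated TEAE restriction.

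If the site instead opens a new entry dated at the worsening, step 1 gives a TEAE and the remaining steps follow. Nothing requires that, and Protocol 4.4.8 lists onset, severity, causality and seriousness once each per AE.

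Partial times do not alter the result for a known earlier onset. When the AE starts on the day of first dose and its time is missing, Appendix 2 imputes the latest possible time, capped at the AE stop time. SAP 17.1 sends unclassifiable AEs to the treatment-emergent side. Both lean towards TEAE, but neither touches an AE that began on an earlier day.

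**The causality conflict.** For the same test case, Protocol 4.4.8 says always unrelated. Protocol 4.4.3 says that if the investigator or sponsor cannot rule out a causal link, that label may not be used. Both cannot be followed once the AE has plausibly been aggravated by the infusion.

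**Size, illustration only.** The documents give no AE rate. Assumptions: 0.05 to 0.2 AEs per subject-week during Screening, of which 5% to 15% are ongoing at dosing and then worsen.

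- Exposure: 60 subjects × 3 weeks = 180 subject-weeks.
- Screening-onset AEs: 180 × 0.05 = 9 to 180 × 0.2 = 36.
- Affected: 9 × 0.05 = 0.45 to 36 × 0.15 = 5.4, both arms together.

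**The case against.** The strongest reply is that little is actually hidden. The event survives in every place listed at step 5, and a serious aggravation would reach the sponsor within 24 hours, be listed, and under Protocol 5.1.4 be described in a narrative. Clinically relevant vital-sign changes during an infusion are reported as AEs in their own right (Protocol 4.3.2 and 5.1.4). Laboratory and vital-sign changes from baseline are summarized whatever the AE onset. All of this stands, and it rules out the inference a reader might draw that such events vanish from every comparative safety table.

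A reader might also infer that the AE is permanently non-emergent and unrelated. The documents do not settle that. A site may open a new entry, the eCRF instructions are not part of these documents, and Protocol 4.4.3 contradicts the always-unrelated note. What stands is that correct classification depends on a site choice the plan does not direct.

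The gap is also narrow. It covers AEs that begin between consent and first infusion and persist to dosing. An illness predating consent is medical history; if it worsens after dosing and is then reported as an AE, its onset would be post-dose.

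Finally, this is a Phase 2 proof-of-concept study with descriptive safety and, by default, no between-group safety tests. No efficacy conclusion turns on this rule. That bears on priority, not on whether the rule is right.

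**Conclusion.** Wrong as written, low priority. The onset-only rule and the always-unrelated note together keep an aggravated pre-infusion AE out of the TEAE, suspected ADR, infusional and serious-TEAE summaries unless the site enters the worsening separately. The note also conflicts with Protocol 4.4.3.

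The number of events is probably small. The range of 0.45 to 5.4 has no support in the documents beyond the 60 subjects and three weeks, and its low end is below one event in the whole trial.

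It is tempting to conclude that the rule flatters IGIV-C. The documents do not show this: the rule is the same in both blinded arms, and it under-counts IGIV-C more than placebo only if the product aggravates AEs already present, which is unknown.

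**What to change.** - **SAP 17.1 and Appendix 2:** state that an AE with onset before the first infusion that increases in intensity or becomes serious on or after the first infusion counts as a TEAE from the date of worsening.
- **Protocol 4.4.8 and the eCRF guidelines:** record that worsening as a new AE entry with its own onset, seriousness and causality. The SAP sentence depends on this, because outside infusions the plan does not require the time of an intensity change to be collected.
- **Note in Protocol 4.4.8:** limit the always-unrelated rating to the pre-infusion episode, which reconciles it with Protocol 4.4.3.

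If recording can no longer be changed, AEs ongoing at the first infusion could be checked at the blinded review meeting described in SAP 5.4. That would recover only those whose worsening is documented.

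The cost is a few sentences, minor recording work and a slightly higher TEAE count.
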